10.6.1.2 Clinical Laboratory Evaluations

Descriptive summaries of clinical laboratory evaluations (hematology, serum chemistry, urinalysis) results will be presented in summary tables by evaluation visit using number of patients (n), mean, median, standard deviation, minimum, and maximum. Changes from baseline will be summarized for each post-baseline visit. The number of patients with clinically significant laboratory results or abnormal results during the study period will be presented in shift tables.

For the laboratory measurements, shift tables will be presented in terms of Low (L), Normal (N), High (H), Missing (M). High and Low measurements will be based on reference ranges provided by the laboratory at the study site.

Clinical laboratory results will also be presented in data listings.

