7.7 Clinical Laboratory Tests

Blood, urine, and CSF samples will be collected as described below for clinical laboratory testing. Procedures for collection and handling of samples are included in the Laboratory and/or Study Operations Manual.

Patients will be in a seated or supine position during blood collection. Clinical laboratory tests will include hematology, serum chemistry, and urinalysis.

Laboratory Parameters

Clinical laboratory tests will be performed at a central laboratory. Clinical laboratory tests will include the following:

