7.8.1.1 Standard Urinalysis

The following urinalysis parameters will be performed at a central laboratory: pH, macroscopic and microscopic evaluations.

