7.8.2.1 Cerebrospinal Fluid Cell Counts

An aliquot of each CSF sample collected will be evaluated for CSF standard chemistries, glucose, protein, and cell counts. These assessments will be performed at the local laboratory.

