11.11 Data Generation and Analysis

The clinical database will be developed and maintained by a contract research organization or an electronic data capture technology provider as designated by Shire HGT. Shire HGT or its designee will be responsible for performing study data management activities.

Adverse events will be coded using MedDRA. Concomitant medication will be coded using WHO-DD. Centralized laboratories will be employed as described in the study manual to aid in consistent measurement of efficacy and safety parameters.

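### Section 10.6.1.2 classifies central-laboratory results as High or Low with the study site's reference ranges, so the primary safety shift tables can misclassify results and depend on site

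*Protocol*

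**What the plan says.** Section 10.6.1.2 (Clinical Laboratory Evaluations) opens by naming its scope: "Descriptive summaries of clinical laboratory evaluations (hematology, serum chemistry, urinalysis) results" are to be tabulated by visit. It then plans shift tables with the classes Low, Normal, High and Missing, and fixes where the limits come from: "High and Low measurements will be based on reference ranges provided by the laboratory at the study site".

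Section 7.7 describes where the tests are run. It defines the term, "Clinical laboratory tests will include hematology, serum chemistry, and urinalysis", and states that "Clinical laboratory tests will be performed at a central laboratory". Section 7.8.1.1 repeats this for urine: "The following urinalysis parameters will be performed at a central laboratory: pH, macroscopic and microscopic evaluations". Section 11.11 gives the reason: "Centralized laboratories will be employed as described in the study manual to aid in consistent measurement of efficacy and safety parameters".

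Amendment 3 (28 August 2012) and Amendment 2 (13 January 2012) carry the same pair of statements.

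**The concern.** A reference range belongs to the method and laboratory that produced it. Section 10.6.1.2 pairs a central result with a range from elsewhere, and that range can differ from site to site. This undoes part of what central testing is meant to achieve.

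Safety is the primary objective, and section 3.1 puts changes in serum chemistry, hematology and urinalysis in the primary endpoint. There are at most 12 patients in three dose groups, without randomization (6.3) and without a data monitoring committee (11.8). No formal test is applied to safety data (10.6.1.1), so readers will rely on descriptive tables. If dose groups happen to be spread unevenly over sites, a site-specific limit could look like a dose-group difference or mask one.

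**Working it through.** The protocol states no figure on this point, so the check sets the sections side by side.

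1. **Same panels in both places.** Section 10.6.1.2 names hematology, serum chemistry and urinalysis. Section 7.7 defines clinical laboratory tests as the same three. The site-range sentence therefore applies to tests that 7.7 assigns to the central laboratory.

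2. **Could locally run tests explain the sentence?** There are two kinds.
   - CSF standard chemistries, glucose, protein and cell counts: section 7.8.2.1 says "These assessments will be performed at the local laboratory". CSF is not among the panels listed in 10.6.1.2.
   - Pregnancy tests: 7.7.2 lists one with serum chemistry, and 7.7.3 has it done locally. Its result is positive, negative or inconclusive, so it has no High or Low.

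   Neither accounts for a High/Low rule covering the three panels.

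3. **Does another section settle it?** Section 11.7.1 collects reference ranges at start-up from the central or the local laboratory, as applicable. It does not say which set feeds the shift tables. Section 10.6.2.2 leaves presentations to the SAP, but on this item the protocol has already stated a rule.

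4. **When does a class change?** Let U_c and U_s be the central and site upper limits for an analyte, and x the central result. The two classifications differ only if x lies between U_s and U_c; the same holds for the lower limits. If the limits agree, nothing changes. If two sites have different U_s, a value between them is High at one and Normal at the other.

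5. **Which outputs are reached?** The L/N/H shift tables are reached directly. Section 10.6.1.1 also flags new values outside the normal range, but names no source for that range, so those flags are reached only if the same ranges are used. Means, medians, minima, maxima, changes from baseline, full listings and adverse event counts do not use the ranges.

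6. **Size.** It cannot be derived, because the protocol prints no limits and no laboratory standard deviations. A purely hypothetical illustration for one analyte assumes normally distributed values and a central range covering the middle 95% (width 3.92 SD, 2.5% above the upper limit). The site's upper limit is assumed lower by a fraction w of that width, so it sits at 1.96 − 3.92w SD. The share of results at or below the central limit that would be called High is (upper tail − 0.025) / 0.975.

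| w | site limit (SD) | upper tail | share reclassified High |
|---|---|---|---|
| 0.05 | 1.764 | 0.0389 | 0.0139 / 0.975 = 1.4% |
| 0.10 | 1.568 | 0.0584 | 0.0334 / 0.975 = 3.4% |
| 0.20 | 1.176 | 0.1198 | 0.0948 / 0.975 = 9.7% |

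A higher site limit works the other way and hides values above the central limit. The values of w are assumed and nothing in the protocol supports any of them.

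**The case against.** The strongest reply is that the sentence is loose wording. Ranges normally arrive with the central laboratory's data, and the programmer would use them. That may happen, but it would depart from the stated rule, and an SAP that followed the protocol would inherit the mismatch. This reply lowers the practical risk without removing the contradiction.

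A second reply is that shift tables are partly self-protecting. If one site's limit applies throughout, a child whose value always lies between the two limits is High at baseline and High later, so no shift appears. This stands in part. The child still sits in the wrong cell, and a value that crosses one limit but not the other still creates or hides a shift.

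A third reply is that the reach is narrow. Section 10.6.1.1 rests safety primarily on adverse events and on clinically notable abnormal values, which is a different criterion from any value outside L/N/H limits. Every value is listed, and with at most 12 patients reclassification is easy. This stands and bears on severity.

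Three stronger readings are tempting, and the protocol does not support them:

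- That the flags *will* be wrong. A class changes only when limits differ and a value falls between them, so *can be* is the most the text allows.
- That each site applies one fixed range while the children age through Month 54, so age-dependent analytes are misclassified. No section says site ranges are fixed or ignore age or sex.
- That a total of false flags follows from multiplying over the 23 serum chemistry analytes and the monthly visits. That would require every analyte's limit to be shifted the same way, by the same fraction, at every visit. Shift tables also count patients, not flags.

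**Conclusion.** The rule is wrong as written. It is a stated source of reference ranges that contradicts sections 7.7 and 7.8.1.1, so it is more than a detail left to the SAP. Followed literally, central results can be misclassified, and classification can depend on site, wherever site and central limits differ and a value lies between them.

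The consequence is limited to descriptive L/N/H classification in the primary safety analysis, plus the 10.6.1.1 flags if they share the ranges. Its size is unknown. A dose-group artefact would additionally need dose groups to be unevenly spread over sites, and the protocol gives no allocation by site. Severity is moderate: a consistency correction that does not threaten the main safety conclusions.

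**What to change.** Replace the sentence in 10.6.1.2 with: *High and Low will be based on the reference ranges, appropriate to the patient's age and sex, of the laboratory that analysed the sample (the central laboratory for hematology, serum chemistry and urinalysis).* State in 10.6.1.1 that the out-of-range flags use the same ranges. If any locally run test such as CSF is classified, use the performing local laboratory's ranges. The age and sex wording is good practice in growing children and does not correct a stated error.

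The cost is one sentence and a cross-reference. No visit, sample or treatment changes. The change should be made before any shift table is produced.

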10.6.1.3 Anti-rhHNS Antibody Formation

Anti-rhHNS antibody formation will be monitored throughout the study. Results will be presented in summary tables by assay methodology used to identify antibodies, number and percentage of positive and negative specimens by evaluation visit and/or study week, and number and percentage of positive and negative specimens overall. The effect of antibodies on other safety parameters will be assessed by presenting summary tables by antibody status. These results will also be presented in data listings.

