8.2.1.1 Day 1 (Pre-treatment) Assessments Performed Prior to Each Dose

- Physical examination
- Height and weight
- Vital signs
- Hematology
- Serum chemistry
- Urinalysis
- Pregnancy testing (applicable females only)
- Neurological examination (performed prior to the administration of anesthesia and the rhHNS IT injection)
- Concomitant medications, therapies, and procedures
- AE assessments

Note: If the HGT-SAN-055 EOS (or HGT-SAN-067 Screening) assessments were performed within 7 days of first intrathecal rhHNS treatment in this study, the pre-treatment assessments described in this section do not need to be completed prior to the first treatment in study HGT-SAN-067.

DAY 1 (PRE-TREATMENT) ADDITIONAL ASSESSMENTS PERFORMED AT MONTHS 12, 24, 36, AND 54

- Head circumference
- Visual and hearing assessments
- Urine heparan sulfate and heparan sulfate derivatives
- Plasma and /or serum heparan sulfate and heparan sulfate derivatives
- Anti-rhHNS antibody testing
- ABR
- MRI of the head
- Full neurodevelopmental testing, including VABS-II (performed prior to the administration of anesthesia and the rhHNS IT injection)
- Children's Sleep Habits Rating Scale
- Child health questionnaire-50
- Child health questionnaire-87
- Infant toddler QOL Questionnaire

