10.2 Determination of Sample Size

Since this is an extension study, sample size is determined by the number of patients who completed HGT-SAN-055 (maximum of 12 patients) and elected to continue treatment with rhHNS in this study

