Appendix 1 Schedule of Events

HGT-SAN-067 Study Assessments for Patients Who Have Received 6 Months of rhHNS Treatment in Study HGT-SAN-055

Assessment	Screening/or HGT-SAN-055 EOS Visit ^k (Month 6 from the start of HGT-SAN-055)	Dosed every 28 (±7) days (ie, Q4W)		Months 12, 24, 36, and 54 (from the start of HGT-SAN-055)	EOS ^f Month 55 (from the start of HGT-SAN-055)	Month 56 Safety Follow-up ^j
		Pre-Tx Day 1 ^a	IT dosing Day 2 (±2)			
Informed Consent/Enrollment		•				
Physical Examination	•	•	•		•	
Height and Weight	•	•			•	
Head Circumference	•			•	•	
Visual and Hearing Assessment				•	•	
ECG	•		• ^b		•	
Vital Signs	•	•	•		•	
Hematology	•	•			•	
Serum Chemistry	•	•			•	
Pregnancy Testing ⁿ	•	•				
Urinalysis	•	•			•	
Leukocyte pellet preparation ^o	•					
Urine Heparan Sulfate and Heparan Sulfate Derivatives	•			• ^c	•	
Plasma and serum Heparan Sulfate and Heparan Sulfate Derivatives	•			• ^c	•	
Anti-rhHNS antibody testing (serum and CSF) ^l	•			•	•	
Auditory Brainstem Response (ABR)	•			•	•	
MRI of the Head	•			•	•	
CSF Sample Collection ^m	•		• ^c		• ^c	
rhHNS dosing: every 28 (±7) days ^{g, d}			•			
Neurological Examination ^h	•	•	•		•	
Full Neurodevelopmental Testing ⁱ	•			•	•	
Children's Sleep Habits Rating Scale	•			•	•	
Child Health Questionnaire-50	•			•	•	
Child Health Questionnaire-87	•			•	•	
Infant Toddler QOL Questionnaire	•			•	•	

HGT-SAN-067 Study Assessments for Patients Who Have Received 6 Months of rhHNS Treatment in Study HGT-SAN-055

Assessment	Screening/or HGT-SAN-055 EOS Visit ^k (Month 6 from the start of HGT-SAN-055)	Dosed every 28 (±7) days (ie, Q4W)		Months 12, 24, 36, and 54 (from the start of HGT-SAN-055)	EOS ^f Month 55 (from the start of HGT-SAN-055)	Month 56 Safety Follow-up ^j
		Pre-Tx Day 1 ^a	IT dosing Day 2 (±2)			
Concomitant Medications, Therapies, and Procedures	•	•	•		•	•
Adverse Event Monitoring	•	•	•		•	•

Abbreviations: ABR = Auditory brainstem response; CSF = cerebrospinal fluid; EOS = end of study ; ECG = electrocardiogram; IT = intrathecal; MRI = Magnetic resonance imaging; TX = treatment

Note: The timing of assessments is calculated from the start of HGT-SAN-055. Therefore, for example, the end-of-study visit, as presented here at Month 54, corresponds to Month 48 in HGT-SAN-067, but represents a total of 54 months of study treatment (48 months in HGT-SAN-067 + 6 months in HGT-SAN-055).

^a Week 1 only, and only performed if >7 days have elapsed since HGT-SAN-055 EOS visit assessments.

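### The overall anti-rhHNS antibody percentage is based on specimens and cannot show what share of patients became antibody-positive

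*Protocol*

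**What the plan says.** Protocol Section 3.1 lists anti-rhHNS antibodies in CSF and serum among the measures of the primary safety endpoint. Section 10.6.1.3 then sets out how antibody results are summarised, by assay methodology:

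- by time point, as the "number and percentage of positive and negative specimens by evaluation visit and/or study week";
- pooled, as the "number and percentage of positive and negative specimens overall";
- against safety: "The effect of antibodies on other safety parameters will be assessed by presenting summary tables by antibody status";
- individually: "These results will also be presented in data listings".

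No number or percentage of antibody-positive patients is named, and antibody status is not defined. Section 10.2 gives the study size as a "maximum of 12 patients". In Appendix 1, antibody testing in serum and CSF is scheduled at the screening visit (the HGT-SAN-055 end-of-study visit, Month 6), in the column for "Months 12, 24, 36, and 54 (from the start of HGT-SAN-055"), and at the end-of-study visit, Month 55.

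The neighbouring safety summaries count patients. Section 10.6.1.1 reports adverse events as numbers and percentages of patients, each counted once per category. Section 10.6.1.2 reports the number of patients with abnormal or clinically significant laboratory results.

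**The concern.** The question for an enzyme replacement therapy is how many treated patients develop antibodies. A pooled specimen percentage answers a different question. It weights each patient by the number of specimens given, and repeated specimens from one patient are likely to agree with each other. A few persistently positive patients and many briefly positive patients can give the same figure. Because specimen numbers depend on time in study, the figure also moves with who leaves early, even when the set of patients who became positive is unchanged.

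The protocol states this denominator itself; it is not a detail left open. An analysis that follows Section 10.6.1.3 to the letter would carry the specimen percentage into the report as the only overall antibody figure for a component of the primary endpoint.

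**Working it through.** The protocol gives no antibody rate, so there is no figure to reproduce. The check is a count of scheduled specimens followed by illustrative arithmetic.

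**Inputs.** At most 12 patients (Section 10.2). Serum time points: Months 6, 12, 24, 36, 54 and 55, which is 6 (Appendix 1). Assumption: one serum specimen per time point.

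**Step 1: weight per patient.** A completer gives 6 serum specimens; 12 completers give 12 × 6 = 72. Each completer therefore counts six times in the overall denominator.

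**Step 2: what one specimen percentage can mean.** Specimen percentage = (patients ever positive × positive specimens each) / 72. Patient percentage = patients ever positive / 12.

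| Patients ever positive | Positive specimens each | Specimens | Patients |
|---|---|---|---|
| 2 | 6 | 12/72 = 16.7% | 2/12 = 16.7% |
| 3 | 4 | 12/72 = 16.7% | 3/12 = 25.0% |
| 4 | 3 | 12/72 = 16.7% | 4/12 = 33.3% |
| 6 | 2 | 12/72 = 16.7% | 6/12 = 50.0% |
| 12 | 1 | 12/72 = 16.7% | 12/12 = 100% |

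No dropout is needed for this.

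**Step 3: effect of early leaving.** Suppose 2 of 12 patients are positive at every test and 10 are never positive, so the patient figure is 16.7% throughout. A patient leaving after Month 12 who attends the end-of-study visit gives 3 specimens (Month 6, Month 12, end of study).

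- The 2 positive patients leave: (2 × 3) / (2 × 3 + 10 × 6) = 6/66 = 9.1%.
- The 10 negative patients leave: (2 × 6) / (2 × 6 + 10 × 3) = 12/42 = 28.6%.

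The ratio is 28.6 / 9.1, or about 3. Both cases are deliberate extremes.

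**Step 4: the by-visit figure.** At a given time point, within one matrix and one assay, each patient gives one scheduled specimen. The by-visit percentage is then in effect a percentage of patients tested at that visit.

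**Step 5: CSF.** Section 7.8.2.3 sets aside an aliquot of each CSF sample for antibody determination, and Section 6.2.2 takes CSF before each injection. Appendix 1 lists antibody testing only at the six time points. If every aliquot were assayed, 48 months would give about 49 CSF specimens per completer (48 monthly doses plus end of study), or about 53 on a 28-day cycle (48 × 365.25 / 12 / 28 = 52.2, plus 1). Section 10.6.1.3 separates results by assay methodology but does not mention matrix. If serum and CSF were also pooled, CSF would supply about 49/55 = 89% to 53/59 = 90% of the denominator. The document does not settle whether either condition applies.

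**The case against.** Several points on the other side stand. The same sentence of the protocol asks first for by-visit results, which are sound. The data are also listed, and with at most 12 patients a reader can count the ever-positive patients from the listing. The analysis is descriptive, Section 10.6.1.1 bases the safety assessment primarily on adverse events and notable vital-sign and laboratory values, and no decision rule uses the overall specimen percentage. These points limit the consequence. They do not make the pooled percentage informative, and a listing does not replace a summary of a primary-endpoint component.

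Two stronger readings are tempting.

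- **Immortal-time bias.** A reader might infer that the tables by antibody status use a fixed ever-positive grouping, so that events before the first positive test are charged to the positive group. If so, a first positive at Month 6, 12, 24 or 36 would place 6/55 = 10.9%, 12/55 = 21.8%, 24/55 = 43.6% or 36/55 = 65.5% of a 55-month follow-up in the wrong group. Section 10.6.1.3 does not say this. Status at the visit, or at the last test before onset, fits the wording equally well and misplaces nothing under that definition. Section 10.6.2.2 leaves planned analyses and presentations to the SAP, which is not at hand.
- **A much larger dropout effect.** Counting only Months 12, 24, 36, 54 and 55, and giving early leavers one specimen each, yields 2/52 = 3.8% against 10/20 = 50%, a 13-fold spread. That leaves out scheduled tests. Section 8.3 asks patients who discontinue after three or more injections to complete the end-of-study visit, although attendance is voluntary for those electing to leave. With that test the figures are 4/54 = 7.4% and 10/30 = 33.3%, about 4.5-fold. With Month 6 as well, they are the roughly 3-fold figures in the working.

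**Conclusion.** The point holds for the overall line only. As written, the pooled antibody percentage counts each patient up to six times in serum and gives early leavers less weight. It cannot separate 2 of 12 from 12 of 12 patients ever positive when 12 of 72 specimens are positive. This rests on the Appendix 1 schedule, one serum specimen per time point and 12 completers; the positivity patterns are illustrations, not predictions.

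The by-visit percentages are not at fault. No immortal-time bias is shown, because antibody status is undefined in time. The finding is a minor one: a better denominator is available at almost no cost, and the study's conclusions do not depend on the present one.

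**What to change.** In Section 10.6.1.3, or in the SAP with a note that it supplements the protocol, replace or accompany the overall specimen percentage with:

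- the number and percentage of patients ever positive from baseline (the first HGT-SAN-055 dose) onward;
- the number and percentage of patients with treatment-emergent positivity, meaning negative before the first HGT-SAN-055 dose and positive later.

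Give both separately for serum and CSF, and by dose group. Keep the by-visit specimen table, within matrix and assay.

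When the safety tables by antibody status are specified, state the timing rule: assign each event to the patient's status at the last test on or before its onset.

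The cost is a few lines of text and minor programming, with no new samples. The treatment-emergent count needs the pre-dose antibody result from HGT-SAN-055, whose protocol is not at hand. Patients without that result should be shown as not evaluable for that line and still counted in the ever-positive line.

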10.6.2 Secondary Analysis

10.6.2.1 Clinical Assessments

The change from baseline in neurocognitive assessment based scores will be examined by dose group. Furthermore, the effect of rhHNS administration on QoL measures will be examined by presenting mean change from baseline across dose groups. Other relevant assessments which might help in the understanding of clinical activity will also be analyzed.

10.6.2.2 Pharmacodynamic Analyses

To determine the effects of rhHNS administration on biomarkers, mean change from baseline will be assessed at selected time points. The heparin sulfate reduction (in CSF and urine) will be examined using mean change and the corresponding 95% confidence interval. The concentration of inflammatory cytokines in serum and CSF will also be examined. Other exploratory biomarkers in CSF, serum, and urine may also be examined.

The effect of anti- rhHNS antibodies on the changes in CSF biomarkers may also be examined by presenting summary tables by antibody status.

The planned analyses and presentations will be defined in the Statistical Analysis Plan (SAP).

